**Causal Lesion Network Guided Treatment of Bipolar Mania
With Transcranial Electrical Stimulation**

NCT #: NCT05445466

June 23, 2025

Protocol Number:	2022P000295
Title:	Causal Lesion Network Guided Treatment of Bipolar Mania With Transcranial Electrical Stimulation
Design:	Double blind, design with baseline, day 5, 1 month and 3 month follow up visits during which transcranial electrical stimulation (tES) was delivered to the right orbital frontal cortex (rOFC) from baseline to day 5 each day (5 days) twice a day for 20 mins. Participants were randomly assigned to either cathodal transcranial direct current (tDCS), 10hz or personalized transcranial alternating current (tACS) conditions to test the effectiveness and feasibility of stimulating the rOFC using a novel targeting methodology consisting of a lesion network guided brain target linked to mania symptoms.
Objectives:	Evaluate the effectiveness and safety of transcranial electrical stimulation for improving the mania symptoms
Enrollment:	14 Individuals
Clinical Sites:	Beth Israel Deaconess Medical Center, Boston, MA
Patient Population:	Male or female outpatients 18-65 years of age patient's diagnosis with either bipolar or schizoaffective disorder, or history of mania as defined by DSM-5 or DSM-IV-TR criteria
Primary and Secondary Outcomes:	Primary Outcomes: Young Mania Rating Scale (YMRS); Altman Self-Rated Mania Scale (ASRM); Average Hospitalizations Secondary Outcomes: Balloon Analogue Risk Task (BART); The Go/No Go Task; Reinforcement Learning Task (RLT); Social Functioning Scale (SFS); Positive and Negative Syndrome Scale (PANSS); Global Assessment of Functioning (GAF); Barret Impulsiveness Scale (BIS); Resting State EEG; Brief Assessment of Cognition (BAC); Montgomery-Asberg Depression Rating Scale (MADRS)
Inclusion Criteria:	
 1. Aged 18-65 years of age 2. Proficient in English 3. Able to give informed consent 4. Meet diagnostic criteria for bipolar disorder or schizoaffective disorder, bipolar type as verified by the SCID 5. History of mania (>1 lifetime episode) 6. Experiencing mild to moderate symptoms of mania 7. No changes to mood stabilizing medications for a period of 2 weeks prior to participation 8. Has not recently participated in tES/TMS treatments

	In addition to the criteria above, participants for this stimulation procedure will be included if they have a history of mania and may or may not be experiencing symptoms currently.

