Tasks/Cognition Testing	X				X	X	X
EEG	X				X	X	X
tES	X	X	X	X	X		
Sensation Questionnaire	X	X	X	X	X		
Self-Reports	X				X	X	X

Study Visits and Details:

Participants will complete baseline clinical, neuropsychological, behavioral tasks and neurophysiological assessments (day 0), short-term follow-up (day 5) and long-term follow-up (1 & 3 month).

Pre-Screening

Subjects will be prescreened. If the subject appears to qualify for the study, they will be invited in for a screening and a baseline visit.

Screening and Baseline Procedures (approximately 3-4 hours)

Screening and baseline procedures will be conducted in the Massachusetts Mental Health Center (MMHC)/ Beth Israel Deaconess Medical Center (BIDMC) in Boston, MA. The urine toxicology screen and pregnancy test will be completed at MMHC or within BIDMC.

- Eligibility pre-screen will include a telephone pre-screening questionnaire that will assess basic inclusion and exclusion criteria.

- Eligibility screening will include a screening questionnaire that will assess more details related to inclusion and exclusion criteria and will be conducted in-person during the clinical diagnostic session (i.e., the first visit to the laboratory).

- Informed consent will be obtained

- Urine toxicology screen

- Urine pregnancy testing for females of childbearing age

Subjects will be informed that if they do not pass the urine toxicology screen (other than prescribed medication), they will be withdrawn from the study and will not receive compensation for the initial visit. This will be made clear in the pre-screening questionnaire.

- tES screening questions for tES participation

- Demographics: Subjects will be asked to provide standard demographic information (age, sex, race/ethnicity, level of education, cohabitation status) using forms employed in previous studies.

- Psychiatric, medical, substance use history and medication review

- Signing a release to allow for access to recent psychiatric records, if confirmation of medications or psychiatric history is necessary

OBJECTIVES

Primary Objective

The primary objective of this study is to evaluate the effectiveness of tES for improving the mania symptoms (YMRS, ASRM and hospitalizations).

Secondary Objectives

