The secondary objective of the study is to evaluate the safety and tolerability of tES targeting the rOFC as well as secondary clinical outcomes including depression, mania, cognition, impulsiveness, electrophysiology outcomes, social functioning and global functioning

Clinical and Cognitive Outcomes: Symptom ratings will be collected using the PANSS, ASRM, YMRS, MADRS, SFS, GAF, BIS and cognition with the BAC

Electrophysiology Outcomes: A reinforcement learning task will be implemented probing the reward feedback mechanisms related to the rOFC. A resting state task will be implemented to measure brain dynamics at rest.

Computerized behavioral tasks: The BART and Go/No Go task will be used to determine the effective targeting of the rOFC and impulsiveness behaviors.

Diagnostic Assessments

Structured Clinical Interview for DSM-IV (SCID)

This is a structured clinical diagnostic screening interview for subjects 15 and older. It is used to diagnose Axis I disorders including modules on depression, mania, psychosis, alcohol and substance use, anxiety, somatic and eating disorders.

Clinical Assessments

Positive and Negative Symptom Scale (PANSS)

The ratings are based on a clinical interview conducted by trained clinical staff, covering all of the items on the rating scale.

- This rating scale is meant to capture many different types of symptoms including positive, negative, and general psychopathology symptoms. The ratings are based on a clinical interview with the participants.
- Ratings should be based on the patient's condition in the past week.
- Always use the manual with anchor points when scoring and do not try to score from your memory of the anchor points or by their headings (mild, moderate or severe).

Altman Self-Rated Mania Scale (ASRM):

The Altman Self-Rating Mania Scale (ASRM) is a brief, self-report questionnaire used to assess the presence and severity of manic symptoms. It is a five-item scale where individuals rate their experiences over the past week, with higher scores indicating greater symptom severity. Self-administered in survey form.

Barret Impulsiveness Scale (BIS):

A brief, self-report questionnaire used to assess the presence and severity of manic symptoms. The scale contains 30 items that measure three main domains: attention impulsivity, motor impulsivity, and non-planning impulsivity.

Montgomery and Asberg Depression Rating Scale (MADRS)**Interviewer:**

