Description of Study Endpoints

Primary Endpoint

Change from baseline to day 5, 1 month and 3 month in clinical measures (PANSS, ASRM) and hospitalizations after 1 week of tES.

Secondary Endpoints

Change from baseline to day 5, 1 month and 3 month in GAF, SFS total score after 1 week of tES. Change from baseline to day 5 and 1 month in MADRS, PANSS, BIS after 1 week of tES. Change from baseline to day 5 and 1 month in voltage and peak frequency for reinforcement learning task measures after 1 week of tES. Change from baseline to day 5, 1 month and 3 month in cognition scores after 1 week of tES. Change from baseline to day 5, 1 month and 3 month in behavioral tasks (BART & Go/No Go) scores after 1 week of tES.

Safety and Tolerability Endpoint

A self-rated questionnaire related to sensations of tES is given to participants after each stimulation.

General Statistical Considerations

All collected study data will be collected on Redcap and processed using R and Matlab software. Descriptive statistics (n, mean, standard deviation, median, minimum and maximum) will be calculated by treatment group and sham group for continuous variables.

Primary Analyses

Primary Analysis of the primary, secondary, and additional efficacy endpoints: Mixed Model Repeated Measures analysis (MMRM)/non- parametric methods will be used to compare using within group differences as well as to determine the difference between the two treatment groups on the primary, secondary and safety endpoints depending on the distribution of the data.

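### The endpoint section makes PANSS primary where the synopsis and primary objective make YMRS primary, leaving the only clinician-rated mania scale without an endpoint definition

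*Combined protocol and SAP*

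**What the plan says.** The plan assigns the primary measures in three places.

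- **Synopsis, Primary and Secondary Outcomes:** "Primary Outcomes: Young Mania Rating Scale (YMRS); Altman Self-Rated Mania Scale (ASRM); Average Hospitalizations". PANSS comes later in the same entry, among the secondary outcomes: "Positive and Negative Syndrome Scale (PANSS); Global Assessment of Functioning (GAF").
- **Objectives, Primary Objective:** the aim is to "evaluate the effectiveness of tES for improving the mania symptoms (YMRS, ASRM and hospitalizations").
- **Primary Endpoint, under Description of Study Endpoints:** here the definition reads "Change from baseline to day 5, 1 month and 3 month in clinical measures (PANSS, ASRM) and hospitalizations after 1 week of tES".

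The Secondary Endpoints paragraph then lists PANSS again, with MADRS and BIS, at day 5 and 1 month only. YMRS is in none of the primary, secondary or safety lists of that section. The Primary Analyses paragraph that follows refers to primary, secondary and additional efficacy endpoints but names no variable.

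The Secondary Objectives add a smaller inconsistency. They include mania among the "secondary clinical outcomes including depression, mania, cognition, impulsiveness, electrophysiology outcomes, social functioning and global functioning", and the next paragraph says "Symptom ratings will be collected using the PANSS, ASRM, YMRS, MADRS, SFS, GAF, BIS and cognition with the BAC".

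**The concern.** The trial is about mania. YMRS carries instructions to the clinician and is the plan's only clinician-rated scale of mania severity. ASRM is self-administered. BIS, which the plan also describes as assessing manic symptoms, is self-report too. PANSS is rated from an interview, but the plan says of it: "This rating scale is meant to capture many different types of symptoms including positive, negative, and general psychopathology symptoms". If the endpoint section governs, the only mania scale left as primary is a self-report, and a scale not described as measuring mania stands beside it.

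The second risk is choice after the fact. The plan has no rule saying which section prevails, so a report could call either YMRS or PANSS primary and cite a section in support. Timing makes this more pressing. The synopsis describes assignment in the past tense ("Participants were randomly assigned to either cathodal transcranial direct current (tDCS), 10hz or personalized transcranial alternating current (tACS) conditions"), so outcome data may already exist. An undated change of wording would not then show that the choice was made blind to results.

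**Working it through.** The plan gives no alpha, power, effect size or sample-size calculation for these endpoints, so there is no stated figure to reproduce. The main check is a comparison of lists.

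| Place | Status given | YMRS | PANSS | ASRM | Hospitalizations |
|---|---|---|---|---|---|
| Synopsis | Primary | yes | no | yes | yes |
| Synopsis | Secondary | no | yes | no | no |
| Primary Objective | Primary | yes | no | yes | yes |
| Primary Endpoint | Primary: day 5, 1 and 3 months | no | yes | yes | yes |
| Secondary Endpoints | Secondary: PANSS at day 5 and 1 month | no | yes | no | no |
| Safety and Tolerability Endpoint | Sensation questionnaire only | no | no | no | no |

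Three things follow.

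1. The synopsis and the Primary Objective agree with each other. The Primary Endpoint differs from both in one measure of three: PANSS stands where YMRS stood.
2. The endpoint section also contradicts itself. PANSS is primary with three follow-up visits and secondary with two.
3. YMRS is named in the synopsis, the Primary Objective, the list of ratings collected and the Clinical Assessments, but not once from Description of Study Endpoints to the end of Primary Analyses. It therefore has no definition as a change from baseline at named visits anywhere in the plan.

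**Illustration of what a free choice of scale is worth.** Take one between-arm comparison with no true effect and test each scale two-sided at 5%. Let the two test statistics be bivariate normal with correlation r. The chance that at least one is significant is

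P = 1 − P(|Z₁| < 1.96 and |Z₂| < 1.96).

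| r | P |
|---|---|
| 0.2 | 0.0964 |
| 0.5 | 0.0907 |
| 0.8 | 0.0781 |

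A single scale named in advance gives 0.05. The 5% level, the normality and the values of r are all assumptions.

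**The case against.** The strongest reply is that this is a slip of the pen. Two statements agree on YMRS, and PANSS is already secondary in the synopsis and in the endpoint section itself, so a sensible reader would put YMRS back. That may well be how it arose, but the documents do not say so, and the slip sits in the only operative definition of the endpoints. Neither the synopsis's general plan to compare symptoms nor the unnamed additional efficacy endpoints would make YMRS primary.

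Some narrower objections stand in part.

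- **The false-positive range is fragile in absolute terms.** Enrollment is 14 and non-parametric methods are allowed. In an assumed 5-versus-5 exact rank-sum comparison, a nominal 5% test has true size 8/252 = 3.2%, and taking the better of two scales gives roughly 5% to 6% by simulation. The relative inflation is similar. The range also covers one comparison only; it is not this trial's overall error rate, since the section has three primary measures at three follow-ups.
- **The list of ratings collected does not assign secondary status.** Only the word mania in the secondary objective is inconsistent, and that is a minor point.
- **Tense is mixed.** Other sections, including the study visits and the statistical considerations, use the future tense. Whether data existed at the time of writing is unknown.
- **Collection of YMRS by visit is inferred.** The Study Timeline marks clinical evaluation at Visits 1, 5, 6 and 7 without naming scales.

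**Conclusion.** The concern holds and must be fixed before analysis. One of the three primary measures differs between sections. The section that defines the endpoints omits YMRS altogether and gives PANSS two roles with different visits. ASRM and hospitalizations are unaffected. This conclusion rests on the text alone and needs no assumption. The rise from 5% to between 7.8% and 9.6% only illustrates the cost of an open choice. YMRS is not missing from the plan as a whole: it remains primary in the synopsis and the Primary Objective, and that is why the correction can follow the plan's own statements.

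**What to change.** 1. In the Primary Endpoint, replace PANSS with YMRS, to match the synopsis and the Primary Objective.
2. List PANSS once in the endpoint section, as secondary. Say explicitly whether the 3-month visit is included, since the two present listings disagree on it.
3. In the Secondary Objectives, remove mania from the secondary clinical outcomes, or state that YMRS and ASRM are primary and appear there only as ratings collected.
4. Date the correction and state whether it was made before anyone had seen outcome data by arm. If it was not, report both the YMRS and the PANSS results and say so.

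The cost is three sentences of wording and one dated statement. No new data should be needed, provided YMRS was given at each clinical evaluation (Visits 1, 5, 6 and 7). The sponsor should confirm this, because the plan does not state YMRS collection by visit.

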Exclusion Criteria:	
 1. Substance abuse or dependence (w/in past 6 months) 2. Those who are pregnant/breastfeeding 3. History of head injury with > 15 minutes of loss of consciousness/mal sequelae 4. DSM-V intellectual disability 5. Having a non-removable ferromagnetic metal within the body (particularly in the head) 6. History of seizures
Statistical Methodology:	Within and between comparisons to statistically detect differences in symptoms, tasks and electrophysiology measures before and after treatment conditions (cathodal tDCS, 10hz and personalized tACS). To determine the effectiveness and feasibility of targeting the rOFC with a novel targeting methodology to engage target outcomes.

Statement: The design, conduct and reporting of this trial shall be conducted in accordance with the protocol, the United States 45 Code of Federal Regulations (CFR) part 46 known as “The Common Rule”, 45 CFR 164.502(d), and 164.514(a)-(c) known as “The Privacy Rule” of the Health Insurance Portability and Accountability Act (HIPAA), and the International Conference on Harmonization (ICH)/Good Clinical Practice (GCP). All Investigators will have documented training in The Collaborative Institutional Training Initiative (CITI Program) in Biomedical Research and GCP.

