Study Rationale: Mania is a core symptom of bipolar disorder involving periods of euphoria, delusions, and overactivity. Mania occurs in multiple medical and psychiatric illnesses and can be refractory to existing treatments. Two recent studies using brain lesion mapping of psychiatrically healthy individuals presenting with mania identified causal locations in the brain, including the orbitofrontal cortex (OFC), dorsolateral prefrontal cortex (DLPFC), and inferior temporal gyrus (ITG), that were associated with new onset mania symptoms. Moreover, these identified brain regions have also been implicated in bipolar mania with specific disruption in network communication between the amygdala and ventro-lateral prefrontal cortex. The OFC is of particular interest because it is a brain structure that is associated with inhibitory control, risk-taking behavior, and reward, which are major behavioral components of mania. Thus, the association between OFC with mania symptoms, inhibitory control, risk-taking behavior and reward suggests that this region could be targeted using noninvasive brain stimulation. While several studies have non-invasively targeted the DLPFC for mania, no study to date has non-invasively stimulated the OFC with either transcranial direct current stimulation (tDCS) or alternating current (tACS) in bipolar disorder and examined its effects on mania, inhibitory control, or risk-taking behavior. However, a study in healthy volunteers showed that cathodal stimulation to the OFC enhanced inhibitory control and decreased risk-taking behavior. Recently, research have showed that targeting the OFC with tACS, personalized to the individual's intrinsic beta-gamma frequency of the reward network, that individuals showed rapid, reversible, frequency-specific modulation of reward-guided choice behavior and learning. Here we aim to answer the question of whether noninvasive brain stimulation when optimally targeted and personalized to an individual's beta-gamma frequency to the OFC can improve emotional cognitive processing and mania symptoms compared to tDCS or sham targeting. The knowledge gained from this study will provide a marker for clinical response and allow personalized treatment for patients with bipolar disorder.

Study Protocol:

Study Timeline

Study Visit Timeline	Visit 1	Visit 2	Visit 3	Visit 4	Visit 5	Visit 6 (1-month follow up)	Visit 7 (3-month follow up)
Consent	X						
Clinical Evaluation	X				X	X	X

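### The Primary Endpoint section names PANSS where the synopsis and primary objective name YMRS, ranks no outcome or visit, sets no error control, and leaves the group comparison unsettled

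*Combined protocol and SAP*

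**What the plan says.** **Outcomes.** The Primary Endpoint section gives "Change from baseline to day 5, 1 month and 3 month in clinical measures (PANSS, ASRM) and hospitalizations after 1 week of tES". The Secondary Endpoints section then adds "Change from baseline to day 5 and 1 month in MADRS, PANSS, BIS after 1 week of tES". YMRS appears in neither section. The synopsis gives YMRS, ASRM and hospitalizations as primary and PANSS as secondary. The Primary Objective also names YMRS, ASRM and hospitalizations.

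**Groups.** The synopsis design row says "Participants were randomly assigned to either cathodal transcranial direct current (tDCS), 10hz or personalized transcranial alternating current (tACS) conditions", and its statistical row refers to comparisons "before and after treatment conditions (cathodal tDCS, 10hz and personalized tACS". Neither mentions sham. The Study Rationale sets personalized stimulation against other options: "compared to tDCS or sham targeting". Under General Statistical Considerations, descriptive statistics "will be calculated by treatment group and sham group for continuous variables".

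**Analysis.** Primary Analyses says "Mixed Model Repeated Measures analysis (MMRM)/non- parametric methods will be used to compare using within group differences" and also plans to determine "the difference between the two treatment groups on the primary, secondary and safety endpoints depending on the distribution of the data". No key visit, alpha, sidedness or multiplicity rule appears anywhere in the document.

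**The concern.** Three outcomes at three visits are all primary, and the section that defines them disagrees with the objective about which scale measures mania. An analyst following the endpoint section would test PANSS, described in the protocol as covering positive, negative and general psychopathology, and would not test YMRS. ASRM would remain, so mania would be assessed in the primary endpoint only by self-report and hospitalizations.

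With nothing ranked, any favourable scale at any visit could be presented as the primary result. The plan does not say whether the repeated-measures model gives one test per outcome or a contrast at each visit, and that choice changes the false-positive risk substantially. The group descriptions do not agree, so a reader cannot tell which arms the between-group comparison involves.

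**Working it through.** **1. Scales, side by side**

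| Section | Primary outcomes | PANSS | YMRS |
|---|---|---|---|
| Synopsis | YMRS, ASRM, hospitalizations | secondary | primary |
| Primary Objective | YMRS, ASRM, hospitalizations | not named | primary |
| Description of Study Endpoints | PANSS, ASRM, hospitalizations | primary and secondary | in no endpoint |

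**2. Groups, side by side**

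| Section | Groups |
|---|---|
| Synopsis (design and statistical rows) | cathodal tDCS, 10 Hz tACS, personalized tACS; no sham |
| Study Rationale | personalized stimulation against tDCS or sham |
| General Statistical Considerations | treatment and sham |
| Primary Analyses | two treatment groups |

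**3. Inputs for the error rate.** The plan states no error rate, so there is no figure to reproduce.
- From the document: 14 participants, three post-baseline visits, two primary rating scales.
- Assumed: two-sided 0.05 per test; two equal groups, 14/2 = 7 each; normal data; no true difference; scale correlation 0 to 0.7; correlation of change scores between visits 0.5 to 0.9.
- Hospitalizations are left out here.

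There are 2 between-group tests if each scale is tested once, and 2 × 3 = 6 if every visit is tested.

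**4. Independence values.** 1 − 0.95² = 0.0975, and 1 − 0.95⁶ = 0.265.

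**5. Why the visits are not independent.** Each endpoint is a change from the same baseline. Suppose the variance σ² is equal at all visits and the raw correlation is ρ between any two. Then:
- Cov(Yj − Y0, Yk − Y0) = σ²(ρ − ρ − ρ + 1) = σ²(1 − ρ)
- Var(Yj − Y0) = 2σ²(1 − ρ)
- Correlation = σ²(1 − ρ) / [2σ²(1 − ρ)] = 0.5

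Visit correlation is therefore taken from 0.5 upwards. A baseline-adjusted analysis could lower it, but the plan does not state one.

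**6. Simulation.** Pooled-variance t-tests, 7 + 7 − 2 = 12 df, critical value 2.179, 100,000 null trials per cell. The Monte Carlo standard error is at most √(0.266 × 0.734/100,000) = 0.0014, or 0.14 percentage points. The table gives the chance of at least one significant result. The second column averages the four runs at each scale correlation.

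| Scale correlation | Each scale once | Every visit, visit corr. 0.5 | 0.7 | 0.9 | Independent visits |
|---|---|---|---|---|---|
| 0 | 9.7% | 23.8% | 21.3% | 16.3% | 26.6% |
| 0.3 | 9.6% | 23.8% | 21.1% | 16.2% | 26.1% |
| 0.5 | 9.2% | 22.7% | 20.0% | 15.6% | 25.0% |
| 0.7 | 8.4% | 20.9% | 18.4% | 14.1% | 23.3% |

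**7. What the table leaves out.** Testing hospitalizations, counting within-group tests, or testing three arms in pairs would all raise the risk. For example, one scale at one visit tested in all three pairs gives 11-12% (assumed split 5/5/4) instead of 5%. A single overall three-group test would not add error in this way.

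**8. After the change.** One scale, one visit and one contrast at 0.05 gives 5%. If several tests must stay primary, Bonferroni thresholds would be 0.05/2 = 0.025 (two tests) or 0.05/6 = 0.0083 (six tests).

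**The case against.** **PANSS is probably a slip for YMRS.** The synopsis and the objective agree on YMRS, and the endpoint section's own secondary list places PANSS where the synopsis does. This stands as the likely explanation. A reader might infer that the mania scale was deliberately removed, but nothing in the document shows that. The text still needs correcting, because the endpoint section is the one an analyst would follow. The listing of mania among secondary clinical outcomes under Secondary Objectives is a loose list of domains and adds little.

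**A contrast is named.** Primary Analyses does refer to the difference between two treatment groups, so it would be wrong to say there is none. The design row could also be read as tDCS against tACS, which would fit two groups. What remains is that sham appears in two sections and is absent from the synopsis, and that the statistical row lists three conditions. The arms being compared and the visit are still not fixed.

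**The trial is small and partly about feasibility.** This softens the case for strict error control. However, the primary objective is effectiveness and the plan calls for comparative testing.

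**Choices made after seeing the data.** The synopsis is partly in the past tense, and a reader might infer that outcome or visit could be selected once results were known. Other sections use the future tense, and the document does not show that data were examined before the analysis was fixed. Verb tense alone does not support that inference.

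**Conclusion.** The point holds on the text. The endpoint section conflicts with the synopsis and objective on the primary scale, lists PANSS twice and omits YMRS. It makes three outcomes at three visits primary without ranking or error control. The between-group comparison cannot be settled while the group descriptions differ.

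Under the stated assumptions, the false-positive risk for the two scales alone is about 8-10% if each is tested once and about 14-24% if every visit is tested. A reader might quote 26% for the second case, but that needs independent visits, which does not fit changes from a shared baseline. The textual conflicts are certain. The rates are indicative, because the document gives no alpha, correlations or allocation. The choice between MMRM and non-parametric methods is a minor matter and not part of this conclusion.

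**What to change.** - Replace PANSS with YMRS in the Primary Endpoint section, or otherwise reconcile that section with the synopsis and the Primary Objective.
- Reconcile the number of groups, and whether there is a sham group, across the synopsis, Study Rationale, General Statistical Considerations and Primary Analyses.
- Name one primary scale (YMRS matches the stated objective), one visit and one between-group contrast, at a stated two-sided alpha. If there are more than two groups, test the contrasts in a fixed order or by Holm.
- Make the other scales and visits and hospitalizations secondary. Report within-group change as estimates with confidence intervals.
- If data have already been examined, label the analysis exploratory and report every test run.

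The cost is mainly wording. YMRS is already among the ratings to be collected, and clinical evaluation is scheduled at baseline and at all three later assessments, so no new data are needed. The downside is that some outcomes and visits lose primary status.

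### Endpoints are defined as change from baseline, but no baseline adjustment is specified; with 14 participants one pooled, baseline-adjusted model should be prespecified

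*Combined protocol and SAP*

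**What the plan says.** Under Description of Study Endpoints, the Primary Endpoint is "Change from baseline to day 5, 1 month and 3 month in clinical measures (PANSS, ASRM"), together with hospitalizations. The Secondary Endpoints take the same form, for example "Change from baseline to day 5, 1 month and 3 month in GAF, SFS total score after 1 week of tES". MADRS, PANSS, BIS, the reinforcement-learning EEG measures, cognition, BART and Go/No Go follow as further changes from baseline. (The synopsis lists YMRS as primary where this section lists PANSS. The point below applies to either scale.)

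The analysis is one sentence under Primary Analyses: "Mixed Model Repeated Measures analysis (MMRM)/non- parametric methods will be used to compare using within group differences", and also "to determine the difference between the two treatment groups on the primary, secondary and safety endpoints depending on the distribution of the data". It gives no fixed effects, covariates or covariance structure. It does not say whether the baseline score is a covariate, a response or absent. The Statistical Methodology row of the synopsis promises within- and between-condition comparisons and adds no covariate.

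The synopsis gives the enrollment as "14 Individuals" and names three active conditions, without an allocation ratio. Inclusion criterion 6 asks for mild to moderate mania symptoms, but a sentence after the list says participants "may or may not be experiencing symptoms currently". The Study Timeline schedules clinical evaluation, tasks and cognition, EEG and self-reports at Visit 1, so baseline scores will exist.

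**The concern.** Subtracting the baseline fixes its slope at 1. When the correlation between baseline and follow-up is below 1, that over-corrects: a condition that happens to draw higher-scoring people will tend to show a larger fall, whatever the treatment does. In a trial of 14 such draws are common. If people with and without current symptoms are both admitted, baseline mania scores may also spread widely.

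The endpoint definition together with an unspecified model leaves two gaps. On the non-parametric route, the ordinary test on change scores is unadjusted unless the plan says otherwise. On the MMRM route, the analyst can decide about baseline after seeing the data. The between-condition result, and the width of its interval, may then depend on a choice the plan does not make.

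**Working it through.** The plan states no power, SD, effect size or correlation, so there is no figure of its own to reproduce.

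**Inputs.** From the documents: 14 participants, three conditions in the synopsis, and two groups in the Primary Analyses sentence. Assumed: allocation as equal as possible; baseline/follow-up correlation rho from 0.2 to 0.8; a linear relation; equal variances at baseline and follow-up; one post-baseline visit at a time.

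**Step 1, group size.** 14/3 = 4.67, so 4-5 per condition (5/5/4). If two groups are meant, 14/2 = 7 each.

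**Step 2, chance imbalance.** The SD of the difference in baseline means, in baseline SDs, is sqrt(1/n1 + 1/n2).

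| Pair | SD of difference | P(more than 0.5 SD) | P(more than 1 SD) |
|---|---|---|---|
| 4 v 5 | 0.67 | 46% | 14% |
| 5 v 5 | 0.63 | 43% | 11% |
| 7 v 7 | 0.53 | 35% | 6% |

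With 5/5/4, the probability that at least one of the three pairs differs by more than 0.5 SD is 73% by simulation; for more than 1 SD it is 28%.

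**Step 3, what reaches the contrast.** Given the baselines, the expected difference in change is the treatment effect plus rho × imbalance minus imbalance, that is, the effect minus (1 - rho) × imbalance. A 0.5 SD imbalance shifts the contrast by 0.7 × 0.5 = 0.35 SD at rho 0.3 and by 0.5 × 0.5 = 0.25 SD at rho 0.5. Averaged over randomizations the shift is zero.

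**Step 4, precision.** The variance of the adjusted contrast relative to the change contrast is (1 + rho)/2 × (1 + 1/(f - 2)), where f = N - number of groups. The second factor is the cost of estimating the slope. Multiplying by (t with f - 1 df / t with f df)² gives the squared CI-width ratio.

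- One pooled three-condition model: f = 11, slope factor 1 + 1/9 = 1.111, t factor 1.025. At rho 0.5 this gives 0.75 × 1.111 × 1.025 = 0.854, and the square root is 0.92.
- One 4 v 5 model: f = 7, slope factor 1 + 1/5 = 1.2, t factor 1.071. At rho 0.5 this gives 0.75 × 1.2 × 1.071 = 0.964, and the square root is 0.98.

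CI width, adjusted divided by unadjusted:

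| rho | Pooled, 3 conditions | 7 v 7 | Separate 4 v 5 |
|---|---|---|---|
| 0.3 | 0.86 | 0.85 | 0.91 |
| 0.5 | 0.92 | 0.92 | 0.98 |
| 0.7 | 0.98 | 0.98 | 1.04 |
| 0.8 | 1.01 | 1.00 | 1.08 |

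Simulation of mean widths agrees for the pooled model: 0.82, 0.86, 0.92, 0.98 and 1.01 at rho 0.2, 0.3, 0.5, 0.7 and 0.8. For separate 5 v 4 models it gives 0.97, 1.03 and 1.06 at rho 0.5, 0.7 and 0.8.

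**Step 5, break-even.** In the pooled model the variances are equal at rho = 2/1.111 - 1 = 0.80; counting the lost degree of freedom, at about 0.76. In separate 4 v 5 models the figures are 2/1.2 - 1 = 0.67 and about 0.56.

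**Step 6, power.** In the pooled 5/5/4 model, simulated power for a 1.5 SD difference between two conditions of five rises from 45% to 58% at rho 0.3, and from about 57% to 65% at rho 0.5.

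**The case against.** The strongest reply is that the plan never says it will skip adjustment. A reader might infer from the endpoint wording that raw changes are compared with no baseline term. The documents do not support that: the model sentence lists no terms at all, and an MMRM of change with baseline as a covariate gives the same treatment contrast as one of the follow-up score. This stands. The defect is non-specification, and it bites hardest on the non-parametric route.

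Four further objections stand in part.

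- **Group size.** Four to five per condition is an inference, because no allocation ratio is given and Primary Analyses speaks of two treatment groups. With 7 v 7, imbalance is less likely (35% beyond 0.5 SD), but the precision ratios barely move.
- **Precision.** A reader might infer that an unadjusted analysis always loses precision. It does not: the gain disappears at high rho, and earlier if conditions are compared in separate pairwise models. There, power for 1.5 SD falls by about 2 points at rho 0.7 and 4 at rho 0.8. With rho unknown and likely to differ between outcomes, a uniform gain is not shown.
- **Bias.** The change contrast is not biased on average. The shift is conditional on the allocation drawn, though one small trial is interpreted on that allocation.
- **Floor.** Mania scores near zero cannot fall, which implies a non-linear relation. The figures above assume a linear one, and a common slope may not remove all of the floor effect. The floor argument concerns the mania scales, not EEG, cognition, GAF or SFS. How many people enter near the floor depends on reconciling inclusion criterion 6 with the sentence that follows the list.

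**Conclusion.** The point holds as a failure to specify. For the scale, task, cognition and EEG endpoints the plan defines change from baseline and does not say whether or how the baseline score enters the analysis. At this sample size a baseline difference above 0.5 SD between some pair of conditions is more likely than not under a 5/5/4 split (73%), and has a 35% chance under 7 v 7. An unadjusted contrast would carry minus (1 - rho) times it.

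The benefit of adjustment in one pooled model is moderate: a 95% CI shorter by about 18%, 14-15%, 8% and 2% at rho 0.2, 0.3, 0.5 and 0.7. These sizes rest on the assumed rho, linearity, equal variances and near-equal allocation. The change should be made, but the silence does not by itself invalidate the trial. Hospitalizations fall outside the point, because no Visit 1 score is scheduled for them.

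**What to change.** In Primary Analyses, prespecify one MMRM over all randomized conditions, fitted to post-baseline scores. Include condition, visit, condition-by-visit and that outcome's own Visit 1 score as a covariate with a common slope, and use Kenward-Roger degrees of freedom. Take all between-condition contrasts from this pooled model, not from separate two-group fits.

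For the non-parametric fallback, name a rank ANCOVA at each visit: regress ranked follow-up on ranked baseline, then compare the residuals across conditions with a permutation test.

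Apply this to every scale, task, cognition and EEG endpoint. Give hospitalizations their own analysis. Keep mean change from baseline as a descriptive table. State the number of conditions and the allocation ratio, so that the condition term is defined.

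The cost is SAP wording and one degree of freedom. No new data are needed. If rho is 0.8 the interval is about 1% wider, and above that there is no gain.
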